13.12.2. Secondary outcomes

[figure not shown]
- **Acceptability of all data collection forms, outcome measurement tools and the PERMIT intervention as a whole:**
 - We will use the weekly debrief with PERMIT champions, interviews with PICU health care professionals and interviews with parents/legal guardians to assess acceptability of all data collection forms, outcome measurement tools and the PERMIT intervention as a whole. These data, along with the data from the data collection forms and outcome measurement tools themselves, will also provide us with an indication of the potential impact of the PERMIT intervention on CYP and parents/legal guardians.
 - **Number of ERM activities prescribed per CYP following patient acuity screening:**
 - The Local PERMIT Research Team will record the number of ERM activities prescribed to CYP follow daily acuity screening daily.
 - **Number of ERM activities delivered per CYP:**
 - The Local PERMIT Research Team will convert prescribed ERM activity to delivered ERM activity and will calculate this on a daily basis.
 - **Safety and adverse event rates during an ERM activity:**
-

17/21/06: The PERMIT Feasibility Study

- The Local PERMIT Research Team will undertake safety and adverse event reporting by day, by patient and by PICU.
- **Safety and adverse event rates throughout the whole PERMIT intervention study period:**
 - The Local PERMIT Research Team will undertake safety and adverse event reporting by day, by patient and by PICU.

17/21/06: The PERMIT Feasibility Study

13.12.3. Figure 2 Overview of primary and secondary outcomes

13.13. Data collection

13.13.1. Weekly debrief with PERMIT champions:

To assess implementation progress within PICUs (e.g. barriers and facilitators to implementation), the Central PERMIT Research Team will conduct the weekly debrief with PERMIT champions either in person or via telephone/video conference. A structured interview schedule (PERMIT_Champion_Debrief_Interview_Schedule_V1_07.12.2020) will be used to guide these informal discussions. The interview schedule is based on the six phases of the PERMIT intervention (i.e. phase 1 'build the team', phase 2 'take stock', phase 3 'get buy-in', phase 4 'get ready', phase 5 'make it work', phase 6 'keep it going'). The weekly debrief will not be audio-recorded or transcribed. The researcher (member of the Central PERMIT Research Team) will make written notes, which he or she will type up. The notes will not include any personal information or any information that could be attributable to individuals taking part. The weekly debrief will continue throughout steps 1-3 of the PERMIT feasibility study.

13.13.2. Surveys of PICU health care professionals:

To assess implementation progress within PICUs (e.g. barriers and facilitators to implementation), PICU health care professionals will complete a brief online survey (PERMIT_Health_Care_Professional_Draft_Survey_V1_07.12.2020) at three time points in the study (i.e. three surveys in total). The survey is based on the Normalization Measure Development Questionnaire (NoMAD). The NoMAD is a 20-item self-report instrument measuring progress with implementation (57). It shows high internal consistency and has been validated in heterogeneous samples across languages and settings (58). Completed surveys are automatically submitted to the Central PERMIT Research Team for processing and analysis.

13.13.3. Interviews with PICU health care professionals:

To assess implementation progress within PICUs (e.g. barriers and facilitators to implementation), the Central PERMIT Research Team will conduct interviews with PICU health care professionals either in person or via telephone/video conference. The interviews will take place within step 3 of the study. A semi-structured interview schedule (PERMIT_Health_Care_Professional_Interview_Schedule_V1_07.12.2020) will be used to guide the interviews. The interview schedule is based on both the preparation phases of the PERMIT intervention (i.e. phase 1 'build the team', phase 2 'take stock', phase 3 'get buy-in' and phase 4 'get ready') and the patient delivery phases (i.e. phase 5 'make it work' and phase 6 'keep it going'). The interviews will last for approximately 30-40 minutes and will be audio-recorded and transcribed for analysis.

13.13.4. CYP clinical data – collected routinely through PICANet:

Currently, all CYP admitted to PICU have data recorded via the Paediatric Intensive Care Audit Network (PICANet). PICANet has permission to collect identifiable patient data under section 251 of the NHS Act 2006 (originally enacted under Section 60 of the Health and Social Care Act 2001). Participating sites already collect data for PICANet and submit this securely to PICANet web. A full list of data items and data definitions can be found at www.picanet.org.uk/documentation.

- For each CYP enrolled into the study the Local PERMIT Research Team will collect NHS number, date of birth and date of PICU admission. The Local PERMIT Research Team will use this information to identify PERMIT study participants on the PICANet web-based system and will insert their unique PERMIT study ID into the system. Each site will then be able to conduct a data download of a pseudo-anonymised dataset pertaining to each individual CYP enrolled into the PERMIT study.

- The data download will include the PICANet minimum dataset for each individual participant. This will include: demographic and socioeconomic data (participant's date of birth, sex, ethnicity, first 4 digits of their post code); pre-PICU health status (past medical history including underlying conditions and co-morbidities); acute illness data (PIM2/PIM3 (model of Paediatric Index of Mortality that assesses the risk of mortality among children admitted to a PICU); PICU admission and discharge diagnoses; co-morbidities; operations and invasive procedures performed; type of admission; PICU and hospital length of stay, duration of mechanical ventilation, high frequency oscillatory ventilation, extracorporeal membrane oxygenation, renal replacement therapy, and vasopressor/inotropic support; sedative medications and days of exposure.

The information will be entered into the PERMIT study RedCAP database.

13.13.5. CYP clinical data – collected in addition to PICANet:

The Local PERMIT Research Team will collect the following data using validated data collection tools (see Appendix 1). The data will be collected daily from time of enrolment into the study until PICU discharge. The information will be entered into the PERMIT study RedCAP database:

- Level of organ dysfunction: PELOD-2 score.
- Level of physical activity: Children's Chelsea Critical Care Physical Assessment Tool (cCPAx).
- Skin integrity: Braden QD will be assessed to assess skin integrity and risk of pressure damage/injury.
- Presence of delirium: Cornell Assessment of Pediatric Delirium (CAPD) or Ps-CAM which is used in conjunction with the Richmond Agitation Sedation Scale (RASS).
- Level of sedation: The COMFORT behaviour scale (COMFORT-B scale) sedation assessment score.
- Pediatric Overall Performance Category (POPC) and Pediatric Cerebral Performance Category (PCPC) (these will be collected at admission to reflect the child's pre-admission status and PICU discharge only).
- In addition, the Local PERMIT Research Team will collect the height and weight of CYP participants from the medical records and pain using a visual analogue scale (collected at PICU admission and discharge, recorded using the PERMIT Case Report Form and entered into the PERMIT study RedCAP database).

13.13.6. PERMIT intervention data:

The Local PERMIT Research Team will use the screening log at each site to collect the following data about the PERMIT intervention:

- **Screening, eligibility and recruitment data:** Daily screening of CYP on PICU by the Local PERMIT Research Team to calculate the number of patients fulfilling inclusion eligibility and number of patients approached, consented/declined for the study.

Once parents/ legal guardians (and CYP where appropriate) have consented patients will receive the PERMIT intervention until PICU discharge. The Local PERMIT Research Team will use the PERMIT Case Report Form for each individual CYP to collect the following data about the PERMIT intervention at ward rounds, ERM intervention sessions and through discussion with local clinicians:

- Patient acuity level
- Prescribed ERM activity level and specific ERM activities

-
- Delivered ERM activity levels and specific ERM activities (including timing, duration, number and type of staff or family member assisting)
 - Reasons for deviating from the prescription, where relevant
 - Use of pause and reassess criteria
 - Safety and adverse events
 - Any intervention / manual tailoring proposed or undertaken within the site

13.13.7. CYP outcome measurement tools:

The Local PERMIT Research Team will collect the following data from parents/legal guardians as the child's proxy using validated outcome measurement tools (see Appendix 1), previously used in the PICU population. The outcome measurement tools will be administered via the preferred communication methods of the parent/legal guardian e.g. face to face, telephone, videoconference, or paper-based or electronic. The information will be entered into the PERMIT study RedCAP database.

CYP outcomes will be measured at two time points:

During PICU admission. Parents/legal guardians will provide a retrospective report based on their child's pre-admission status (two weeks before) by completing: (1) Pediatric Quality of Life Inventory PedsQL™ Infant Scales Version 4.0 – Acute (Aged: 1-23 months) OR PedsQL™ Generic Core Scales Version 4.0 - Acute (Aged: 2 years+); and (2) PedsQL™ Multi-dimensional Fatigue Scale Version 3.0 - Acute

At point of PICU discharge or within 30 days post admission to PICU. Parents/legal guardians will report based on their child's current status by completing: (1) Pediatric Quality of Life Inventory (PedsQL)™ Infant Scales Version 4.0 – Acute (Aged: 1-23 months) OR PedsQL™ Generic Core Scales Version 4.0 - Acute (Aged: 2 years+); and (2) PedsQL™ Multi-dimensional Fatigue Scale Version 3.0 - Acute; and (3) The PedsQL™ Pediatric Pain Questionnaire (PPQ)™ will also be completed at this second time point.

13.13.8. Parent/legal guardian outcome measurement tools:

The Local PERMIT Research Team will collect the following data from parents/legal guardians using validated outcome measurement tools (see Appendix 1). The outcome measurement tools will be administered via the preferred communication methods of the parent/legal guardian e.g. face to face, telephone, videoconference, or paper-based or electronic. The information will be entered into the PERMIT study RedCAP database.

Parent/legal guardian outcomes will be measured at two time points:

During PICU admission. Parents/legal guardians will provide a retrospective report based on their own and families pre-admission status (two weeks before) by completing: (1) Parents/legal guardians will report based on their child's current status by completing: (1)The PedsQL™ Family Impact Module Version 2.0;

At point of PICU discharge or within 30 days post admission to PICU. Parents/legal guardians will report based on their child's current status by completing: (1)The PedsQL™ Family Impact Module Version 2.0; (2) Parent Stressor Scale: PICU; (3) The EMpowerment of PArEnts in The Intensive Care - 30 Item Version (EMPATHIC-30); and (4) Patient Health Questionnaire-4 (PHQ-4).

Interviews with parents/legal guardians of CYP receiving the PERMIT intervention

The Central PERMIT Research Team will conduct interviews with these parents/legal guardians to assess the acceptability of the PERMIT intervention, related data collection and outcome measurement tools and future trial designs. The interviews will be conducted towards the end of the

CYP's PICU stay, or following PICU discharge (up to 30 days after PICU admission), which will usually fall within step 3 of the study. Interviews will be offered via as many different means and as flexibly as possible. They will predominantly be offered via telephone or video-conference (e.g. Zoom). However, depending on the location of the researcher from the Central PERMIT Research Team, they can be offered face to face provided compliance with COVID-19 guidance can be undertaken. A semi-structured interview schedule (PERMIT_Parent_Legal_Guardian_Interview_Schedule_AB_V1_07.12.2020) will be used to guide the interviews. The interviews will last for approximately 30-40 minutes and will be audio-recorded and transcribed for analysis.

13.13.9. Interviews with parents/ legal guardians of CYP who decline for their child to receive the PERMIT intervention:

The Central PERMIT Research Team will conduct interviews with these parents/legal guardians to better understand their decision making, views of ERM and the potential feasibility of future trial designs. The interviews will be conducted similarly to the interviews with parents/legal guardians as described above, using a semi-structured interview schedule (PERMIT_Parent_Legal_Guardian_Interview_Schedule_C_V1_07.12.2020).

17/21/06: The PERMIT Feasibility Study

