CYP (outcome measurement tools)	Pediatric Quality of Life Inventory (PedsQL) TM Infant Scales Version 4.0 – Acute (Aged: 1-23 months) OR PedsQL TM Generic Core Scales Version 4.0 - Acute (Aged: 2 years+)	Local PERMIT Research Team collect the data from parents/legal guardians	36 items / <7min 45 items / <10 min 21/23 items / <5 min	3	Twice per participant	X ¹		X
	PedsQL TM Multi-dimensional Fatigue Scale Version 3.0 - Acute		18 items/ 5 min	3	Twice per participant	X ¹		X
	PedsQL TM Pediatric Pain Questionnaire (PPQ) TM		1 item / <1 min	3	Once per participant			X
Parent/legal guardian (interview)	Interview	Central PERMIT Research Team	≤60 mins	3	Once per participant			X
Parent/legal guardian (outcome measurement tools)	Parent Stressor	Local PERMIT Research Team (collected with validated tools)	30 items / 10 mins	3	Once per participant		X	
	Scale: PICU							
	EMPATHIC-30		30 items / <15 mins	3	Once per participant		X	
	PedsQL TM Family Impact Module Version 2.0		36 items / 5 min	3	Twice per participant	X ¹		X
	Patient Health Questionnaire-4 (PHQ-4)		4 items / 2 min	3	Once per participant			X

[figure not shown]
¹ Baseline pre-PICU score will be calculated retrospectively.

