required to indicate how much of a problem each item has been over the past 7 days on a scale of 0 = “never a problem” to 4 = “almost always a problem.” Items are reverse scored, averaged, and transformed to a scale of 0 to 100, with higher scores indicating fewer problems. In addition to the individual scale scores, it is possible to compute the total score (the mean of the four scale scores), the physical health summary score (equivalent to the physical functioning scale score), and the psychosocial health summary score (the mean of items on the three scales addressing emotional, social, and school functioning). The **PedsQL Infant Scales** are used for children <2 years of age and consist of 36-45 items, depending on age, with 5 domains: physical functioning, physical symptoms, emotional functioning, social functioning, and cognitive functioning. Like the Generic Core Scales, the Infant Scales generate a total score. Both sets of instruments have good validity and reliability, have been widely used, (70-77) and can be completed in 5-7 minutes.(2, 77-79) The instruments can discriminate between healthy children and those with a wide range of acute and chronic health conditions. Norms based on large community samples exist for children in the United States(80), including from 9,467 healthy children in California 3,652 children with a chronic health condition(81) and condition-specific results from >2500 children with one of 10 chronic conditions (e.g., asthma, cancer, cerebral palsy, rheumatologic disease, or end-stage renal disease),(82) and >5000 children and young adults with diabetes.(83)

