8. **PedsQL™ Multi-dimensional Fatigue Scale – Acute Version** (84) is an 18-item scale that encompasses three domains: (1) General Fatigue (6 items, e.g., “I feel tired.”; “I feel too tired to do things that I like to do.”), (2) Sleep/Rest Fatigue (6 items, e.g., “I feel tired when I wake up in the morning.”; “I rest a lot.”), and (3) Cognitive Fatigue (6 items, e.g., “It is hard for me to keep my attention on things.”; “It is hard for me to remember what people tell me.”). The instructions ask how much of a problem each item has been during the past 7 days.(85) The PedsQL™ Multidimensional Fatigue Scale comprises parallel child self-report and parent proxy-report formats. Child self-report include ages 8–12, and 13–17 years. Parent proxy-report includes ages 2–4 (toddler), 5–7 (young child), 8–12 (child), and 13–17 (adolescent), and assesses parent’s perceptions of their fatigue. Cognitive functioning for infants 1-24 months are included in the PedsQL Infant Scale. Items for each of the forms are essentially identical, differing in developmentally appropriate language, or first or third person tense. The format, instructions, Likert response scale, and scoring method are identical to the PedsQL™ 4.0 Generic Core Scales, with higher scores indicating better HRQOL (lower fatigue symptoms).(84-88)
9. **PedsQL™ Pediatric Pain Questionnaire** is a generic symptom-specific instrument to measure pain in patients with acute and chronic health conditions. We will use question #1 and #2, which asks participants capable of self-reporting to identify a point on a 100 mm line that best shows the worst pain the subject experienced ‘now’ and ‘in the past week’. Anchors include “no hurting, no discomfort, or no pain” and “hurting a whole lot, very uncomfortable, severe pain”.
10. **Pediatric Cerebral Performance Category (PCPC)** and the **Pediatric Overall Performance Category (POPC)** quantify short-term cognitive impairments and functional morbidity.(89, 90) The POPC scale is dependent on the PCPC scale, as the PCPC status is included in POPC. Scores range from 1 to 6 for both scales with 1: good, 2: mild disability, and 6: brain death. Studies of patients with scores of 1–4 at PICU discharge, hospital discharge, and one- and six-month follow-up show association with the Stanford Binet Intelligence Quotient, Bayley scales, and Vineland Adaptive Behaviour Scale. (89-92).

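### The baseline questionnaire instructions conflict on which period parents should describe, so some pre-PICU baseline scores may describe the PICU stay

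*Protocol*

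**What the plan says.** Protocol 13.13.7 places the first administration of the child tools (PedsQL Infant or Generic Core Scales, and the Fatigue Scale, all Acute versions) during the PICU admission and defines its content: "Parents/legal guardians will provide a retrospective report based on their child's pre-admission status (two weeks before) by completing" these forms.

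Appendix 1 (13.25.1) describes two of the same instruments differently. For the Generic Core Scales the informant is "required to indicate how much of a problem each item has been over the past 7 days on a scale of 0" upwards. For the Fatigue Scale, "The instructions ask how much of a problem each item has been during the past 7 days".

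For the Family Impact Module, 13.13.8 opens the baseline instruction in the same way: "Parents/legal guardians will provide a retrospective report based on their own and families pre-admission status (two weeks before) by completing". The sentence then continues with a second instruction: "1) Parents/legal guardians will report based on their child's current status by completing: (1)The PedsQL™ Family Impact Module Version 2.0".

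The table in 13.13.10 marks all of these tools in its pre-PICU baseline column. Its footnote says only: "Baseline pre-PICU score will be calculated retrospectively". It names no period.

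**The concern.** A retrospective baseline means something only if every parent describes the same period, and that period ends before the illness that brought the child to intensive care. Here the parent answers while the child is in PICU. A form that looks back from the day of completion therefore reaches into the stay, and an instruction to report the present describes nothing else.

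Two sites could both comply with the protocol and collect different things under one label, one recording the child before admission and the other a child in intensive care. Analysis cannot separate the two afterwards. A form can also be fully completed, and count towards the completion outcome in 13.12.1, while describing the wrong period. Section 13.20.3 speaks of participants who improve on the study outcome measures; for these tools, improvement from baseline can be read only if the baseline period is known.

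**Working it through.** The protocol gives no figure to reproduce. The check compares the texts and then illustrates the size.

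**Comparison by tool**

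| Baseline tool | Period in 13.13.7 or 13.13.8 | Other period stated |
|---|---|---|
| PedsQL Generic Core (age 2 and over) | pre-admission, two weeks before | 7 days (Appendix 1, item 7) |
| PedsQL Fatigue Scale | pre-admission, two weeks before | 7 days (Appendix 1, item 8) |
| PedsQL Infant Scales | pre-admission, two weeks before | none |
| Family Impact Module | pre-admission, two weeks before | the child's present state (same sentence) |

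Each conflict is between two periods, and no tool carries all three. The seven-day conflict is documented for the Core and Fatigue scales only.

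The added clause on the Family Impact Module matches the wording of the discharge/30-day instruction just below it. It repeats the item number (1), and it asks about the child on a form about the family. It looks like a copying slip.

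The phrase two weeks before is itself open. It could mean a point two weeks before admission, the fortnight up to admission, or two weeks back from completion.

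**Illustration**

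- L = recall window in days, counted back from completion. L = 7 is from Appendix 1.
- d = days from admission to completion. This is an assumption. Section 13.13.7 says only that completion is during the admission. Section 13.11.6 has parents approached on day 1 or 2 where possible. Under 13.11.7, parents who first agreed only to the intervention may be re-approached for the outcome tools up to 30 days after admission.
- Share of the window inside the stay = min(d, L) / L.

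For L = 7:

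- d = 1: 1/7 = 14%
- d = 2: 2/7 = 29%
- d = 3: 3/7 = 43%
- d = 5: 5/7 = 71%
- d = 7 or more: 7/7 = 100%

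If two weeks were also counted back from completion (L = 14):

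- d = 2: 2/14 = 14%
- d = 7: 7/14 = 50%
- d = 14 or more: 14/14 = 100%

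If the window is anchored to admission and ends there, the share is 0 whatever d is. Under the current-status instruction, the whole report concerns the stay. Days of illness before admission would come on top of these shares.

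**The case against.** The intent is not in doubt. Sections 13.13.7 and 13.13.8 both ask for a retrospective pre-admission report, and the table column and footnote agree. Appendix 1 describes published instruments in general and is not an administration instruction. The extra clause in 13.13.8 is evidently a slip that the table resolves. The baseline forms are not in the document, so nobody can say what is printed on them, and 13.11.7 has the local team supporting parents through the tools. All of this stands, and it limits the point to wording. It does not remove the point: sites work from the operative text, one sentence of which gives two instructions, and the protocol is silent on how a seven-day form is to yield a pre-admission answer.

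A reader might also infer more than the documents support:

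- *Every baseline questionnaire carries three contradictory periods.* None does. Appendix 1 gives no recall period for the Infant Scales or the Family Impact Module.
- *Baseline and follow-up forms will commonly cover the same days.* A form completed on day 3 and repeated on day 5 would share 5 of 7 days, but both days are assumed, and 13.13.8 allows the second form at discharge or at any time up to 30 days after admission. The length-of-stay shares in 8.12 (40-45% staying at least 3 days, 20% more than 7) are national figures from the Phase 1b plan. They do not fix when either form is completed in Phase 3.
- *The feasibility conclusion falls.* The primary outcome in 13.12.1 is the proportion of tools completed, which does not depend on the recall period. Analysis of these measures is descriptive (13.20.2), in a planned 30 children. POPC and PCPC give a separate record of pre-admission status (13.13.5).

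**Conclusion.** The point holds as a conflict in the baseline instructions. For the Generic Core and Fatigue scales, the protocol's pre-admission period disagrees with the seven-day recall it ascribes to the forms, with no statement that the wording is adapted. For the Family Impact Module, one sentence asks for two different periods.

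If the form wording is followed, between 1 and 7 of the 7 recalled days fall inside PICU for completion from day 1 to day 7, and all 7 after that. If the stray clause is followed, the whole Family Impact Module report does. These sizes rest on assumed completion days and on the form or clause being followed in place of the stated pre-admission intent.

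What is at risk is the meaning of the baseline scores and of any improvement measured from them. The primary completion proportion and the sample size do not change. The correction should be made before data collection, because the intended values cannot be recovered later.

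**What to change.** 1. In 13.13.7, state one reference period for all baseline tools, anchored to the date of PICU admission. Say whether two weeks before means the fortnight up to admission or a point two weeks earlier. The documents do not settle this, so the study team must choose.
2. In the same place, state that the recall wording on the baseline forms, including the seven-day wording of the Generic Core and Fatigue scales, is re-anchored to that period, subject to the instrument owner's agreement.
3. In 13.13.8, delete the second instruction from the baseline sentence, which now runs "pre-admission status (two weeks before) by completing: (1) Parents/legal guardians will report based on their child's current status by completing". The Family Impact Module then follows the same pre-admission period, and the current-status wording stays only at the discharge/30-day time point.
4. Record the date on which each baseline form is completed, so that its distance from admission is known.

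The cost is one clarifying statement, one deletion, one date field and an approach to the instrument owner. The downside is slightly longer parental recall and a small departure from the standard recall wording of validated instruments.
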